# **LIST OF ABBREVIATIONS**

ABBREVIATION/TERM	DEFINITION
AE	Adverse Event
CFR	Code of Federal Regulations
CRF	Case Report Form
EDC	Electronic Data Capture
EOS	End of Study
FDA	Food and Drug Administration
FDF	Financial Disclosure Form
GAIS	Global Aesthetic Improvement Scale
GCP	Good Clinical Practice
ICF/ICD	Informed consent form/ Informed consent document
ICH	International Conference on Harmonization
IEC	Independent Ethics Committee
IRB	Institutional Review Board
ITT	Intent To Treat
IQIS	Investigator Quartile Improvement Score
MTZ	Microthermal treatment zone
PI	Principal Investigator
QA	Quality Assurance
QC	Quality Control
QHS	Every Night At Bedtime
SAE	Serious Adverse Event
UADE	Unanticipated Adverse Device Effect
UV	Ultraviolet
VAS	Visual Analog Scale

# 1. STUDY SYNOPSIS

Name of Sponsor/Company	Bausch Health Americas, Inc.			
Name of Device	CLEAR + BRILLIANT TOUCH® diode laser 1440-nm and 1927-nm			
Title of Study	A Prospective, Single-Center Study Evaluating the Safety and Effectiveness of the CLEAR + BRILLIANT TOUCH® diode laser 1440-nm and 1927-nm Combination Wavelength Treatment.			
Number of Clinical Centers	Single Center			
Study Design	This is a prospective study of up to 30 subjects designed to assess the safety and effectiveness of a non-ablative fractional laser combination wavelength treatment for general resurfacing of photoaged skin. All study subjects will be treated on the whole face with the CLEAR + BRILLIANT TOUCH® 1440-nm and 1927-nm handpieces. Subjects will be treated with a consecutive series of four (4) treatments spaced 1 month apart, along with follow-up study visits at one (1) and three (3) months after final treatment.			
Study Population	To be eligible for the study, the subjects must have mild (I) to moderate (II) photoaging by Glogau Photodamage Scale, no more than fine wrinkles and mild elastosis by Fitzpatrick Wrinkle and Elastosis Scale (Class I-II, Score 1-6). Both males and females will be considered, between the ages 18 and 65 years and Fitzpatrick skin Types I-VI with 70% skin types I-III and 30% skin types IV-VI.  Number of subjects: Up to 30 subjects who meet all study inclusion/exclusion criteria will be considered for entry.			
Study Objective	The objective is to evaluate the effectiveness and safety of the CLEAR + BRILLIANT TOUCH® diode laser combination treatment of 1440-nm and 1927-nm.			
Study Endpoints	Primary Effectiveness Endpoint: improvement in the appearance of at least one measurement of photoaging damage (fine wrinkles, skin texture, dyschromia/pigment, skin radiance, pore size or overall appearance) by the investigator using the quartile improvement score comparing standard 2D baseline photograph captured via Canfield VISIA CA system and the 3 months post final treatment photograph. Reported percent change in improvement.			
	Secondary Effectiveness Endpoint: improvement in the appearance of at least one measurement of photoaging damage (fine wrinkles, skin texture, dyschromia/pigment, skin radiance, pore size and overall appearance) by the investigator using the quartile improvement score comparing standard 2D baseline photograph captured via Canfield VISIA CA system to 1 month post final treatment photograph. Reported percent change in improvement.			
	Safety:			
	
 
Serious Adverse Events (SAEs) related and unrelated to the treatment procedure or to the CLEAR + BRILLIANT TOUCH® diode laser system.
 
			
	
 
The severity of post-treatment skin responses:         
 
Immediate post-treatment erythema and edema.
 
Prolonged post-treatment erythema, edema, dryness/flakiness, hypopigmentation, hyperpigmentation, blistering, scarring.
 
 
 
The evaluation of pain and discomfort immediately after the treatment (within 60 minutes) as reported by the subject on a visual analog scale (VAS)
 
			

Protocol [V01-CBT-401] Bausch Health Americas, Inc.

#### **Exploratory Endpoints**

Subject Modified Global Aesthetic Improvement Scale (GAIS) comparing their overall appearance in photos at 3 months post treatments with baseline photos.

Subject Satisfaction with procedure recorded at 3 months post treatments.

Five (5) patients will have 3 punch biopsies from an area of photoaging comparing baseline to 14 days and 3 months post treatments (location on the face at discretion of investigating physician either pre-auricular or at temple hairline. If face location unattainable the forearm exposed to photoaging may be used as an alternate biopsy location).

Blinded Investigator: analysis of unmarked 2D photo sets via Canfield clinical system. Reviewers will select the order of baseline and post treatment onemonth photos. Then based on their selection assess photos for percentage improvement in photoaging damage using the quartile improvement scale and score 0-4. Reported percent change in improvement of correct order sets.

Blinded Investigator: analysis of unmarked 2D photo sets via Canfield clinical system. Reviewers will select the order of baseline and post treatment threemonths photos. Then based on their selection assess photos for percentage improvement in photoaging damage using the quartile improvement scale and score 0-4. Reported percent change in improvement of correct order sets.

#### 2. INTRODUCTION: BACKGROUND INFORMATION

Skin is susceptible to aging, much like all the other organs of the body. There are two different processes at work that lead to skin alterations. Intrinsic aging is a chronological, biological progression of degenerative changes associated with time, gravity, hormones, and genetics. Exposure to environmental factors contributes significantly to the aging process of the skin. The second process called extrinsic aging is a direct consequence of external elements, mainly induced by chronic exposure to ultraviolet (UV) radiation, and hence called photoaging. UV changes vary considerably among different Fitzpatrick skin types and ethnicity. 1

Extrinsic aging occurs in habitually exposed areas of the body such as face, neck, chest, and arms. Alterations in the skin from photoaging include uneven pigmentation, telangiectasia, wrinkles, roughness (textural changes), and occur in both the epidermis and dermis. Histologically damage to the skin's dermal connective tissue occurs because of the loss of collagen, elastosis, and alterations of components in the extracellular matrix. Increased and uneven pigmentation in photoaging are mostly a result of changes in melanocytes located in the basal epidermal layer.

Patients seek out treatment options for both intrinsic and extrinsic skin concerns for general skin resurfacing. Laser treatments for photoaging began with ablative  $CO_2$  (10,600 nm) lasers, which vaporized the epithelium and heated the dermis. These treatments had prolonged downtime and an increased risk of side effects. Non-ablative lasers were created to spare the epidermis and stimulate collagen in the dermis; they had a better safety profile; however, efficacy was limited.

Non-ablative fractional lasers utilize different wavelengths to ablate or coagulate tissue in columns or microthermal treatment zones (MTZs). Tissue is not vaporized and the stratum corneum remains intact. The skin then heals from both the edge of the wound and underlying tissue. The dermis undergoes necrosis leaving a dead space to be filled with new collagen and repair of tissue related to photoaging. The spared areas shortened downtime and presented a smaller range of side effects, increasing the safety profile. Fractional resurfacing treatments utilizing multiple wavelengths in a single session over a series of treatments has clinical benefits for treating superficial and underlying dermal effects associated with photodamage.

[figure not shown]
The CLEAR + BRILLIANT TOUCH® diode laser is a low powered and low density (0.9- 2.5 watt) non-ablative fractional diode laser that targets water as its chromophore. The system utilizes the principle of fractional photo thermolysis which means only limited areas of the skin are exposed to laser optical energy at one time. Healing time is minimized because the fractional photo thermolysis laser affects only a pre-determined percentage of the skin surface at any one time and does not cause full epidermal wounds. It can deliver a 1927 nm (170  $\mu$ m fixed depth) and 1440 nm (280-390  $\mu$ m depth) wavelength depending upon the handpiece desired while using the same credit key during a session.

In this study, the effect and safety of delivering two wavelengths in the same session treatment, over a series of four treatments addressing alterations of photoaging using the CLEAR + BRILLIANT TOUCH® fractionated diode laser, will be assessed.

### 2.1 Device Description

The CLEAR + BRILLIANT TOUCH® System is manufactured by Solta Medical, Inc. ([name]) and is indicated for use in dermatological procedures requiring the coagulation of soft tissue and general skin resurfacing procedures. The CLEAR + BRILLIANT TOUCH® System consists of a console and two versions of the laser handpiece. The console connects to the facility power source and the handpieces produce laser energy delivered through removable, disposable treatment tips. A credit key is required to activate treatments and is inserted into the side of the console. Additional details on the CLEAR + BRILLIANT TOUCH® System can also be found in the CLEAR + BRILLIANT TOUCH® Laser System User Manual Revision D provided by the Sponsor.

The system includes the Original Handpiece (1440 nm) and the Perméa™ Handpiece (1927 nm), allowing for targeted treatment of different tissue depths.

	Control/Connection/Description	Function
1	Credit Key	Contains treatment credits. Credit Keys are removable and are to be disposed of when finished.
2	Emergency Stop Switch	Stops the laser treatment beam when pressed during an emergency. To restart, twist the button and release it from the latched Off position.
3	Console	Houses the electro-mechanical components that operate the system.
4	Touch Screen	Displays information on operating the system, including system status, progress of the self-test, instructions, and general messaging. The Touchscreen is interactive: Select by tapping the onscreen buttons.
5	Power Button	Powers on and off the system.
6	AC Power Inlet, Network Connection, and USB Ports	Connects the Console to the Power Cord. Used by Solta Medical Maintenance. Downloads Charting information and used by Solta Medical Maintenance.
7	Handpieces	Generate laser energy, and where the Treatment Tips are attached. Two Handpieces are available: The Original Handpiece (1440 nm) in gray, and the Perméa™ Handpiece (1927 nm) in blue.
8	Handpiece Connection Ports	Connect the Handpieces to the Console. Disconnect using the workable latches.
9	Cradle	Holds the Handpieces when they are not being used. Installed Handpieces need to be resting in the Cradle when the self-test runs during the initialization of the system. This is automatically controlled by the software.

Page 12 of 49

### 2.1.1 Mechanical Specifications

Size	31.75cm (W) x 28.58cm (L) x 27.94cm (H)
	12.5" (W) x 11.25" (H) X 11" (D)
Weight	Approximately 15.5LBS (7kg)
Power Cord length	3m (10ft)
Handpiece Cable length	2m (6.6ft)

### 2.1.2 Laser Safety Standards

The CLEAR + BRILLIANT TOUCH® System meets applicable electrical and laser safety standards (per IEC 60601 series and IEC 60825-1) for a Class 1C laser.

The CLEAR + BRILLIANT TOUCH® System contains a Class 1C laser, according to IEC/EN 60825-1 standards. The user and associated staff must take precautions to prevent direct exposure of laser energy to the eyes.

Handpiece Technical Specifications:

Original Handpiece (1440 nm)				
Equipment classification IEC 60601-1	Class 1			
Handpiece	Type BF Applied Part			
IEC 60825-1 Classification	Class 1C – Invisible Laser Radiation			
Wavelength	1440 ± 20 nm; min:1420 max:1460			
Maximum Power (average)	2.5 W			
Maximum Pulse Energy	9 mJ			
Maximum Pulse Width	3 ms			
Pulse Repetition Rate	< 400 Hz			

Perméa™ Handpiece (1927 nm)				
Equipment classification IEC 60601-1	Class 1			
Handpiece	Type BF Applied Part			
IEC 60825-1 Classification	Class 1C – Invisible Laser Radiation			
Wavelength	1927 ± 20 nm; min:1907 max:1947			
Maximum Power (average)	0.9 W			
Maximum Pulse Energy	5 mJ			
Maximum Pulse Width	5 ms			
Pulse Repetition Rate	< 150 Hz			

Page 13 of 49

### 2.1.3 Study Device Accountability

The Investigator will be responsible for keeping current and accurate device accountability records. At various time points throughout the study and/or upon completion of the study, the Sponsor or Sponsor's representative will review and verify the Investigator's accountability records.

Credit Keys and disposable Treatment Tips are used to restrict access to the device to only authorized users. Laser light can only be produced by the system when a valid Credit Key with available treatment credits is inserted into the Console and a Treatment Tip is attached to the Handpiece. One Credit Key is loaded with 12 treatment credits. The Investigator will be provided with sufficient Credit Keys /Treatment Tips to provide treatment for subjects enrolled into the study. Credit Key lot number and Treatment Tip lot number will be recorded for each subject treatment on the CRF.

Following study completion, study devices must be returned to the Sponsor. The Sponsor will be responsible for complete study accountability, returns, and reconciliation of the returned devices at the conclusion of the study.

### 3. STUDY OBJECTIVE:

The objective is to evaluate the effectiveness and safety of the CLEAR + BRILLIANT TOUCH® diode laser combination treatment of 1440-nm and 1927-nm.

### 4. STUDY DESIGN AND ENDPOINTS

#### 4.1 Description of Study Design:

This is a prospective, non-randomized study of up to 30 subjects designed to assess the safety and effectiveness of a non-ablative fractional combination laser wavelength procedure for general resurfacing of photoaged skin. All study subjects will be treated on the whole face with the with the CLEAR + BRILLIANT TOUCH® diode laser 1927-nm & 1440-nm handpieces. Subjects will be treated with a consecutive series of four (4) treatments spaced 1-month apart, along with follow-up study visits at one (1) and three (3) months after final treatment. As primary and secondary effectiveness endpoints aim to evaluate improvement in photoaging damage post-treatment as compared to baseline following treatment with the FDA-cleared CLEAR + BRILLIANT TOUCH® System, no control group will be utilized.

### 4.2 Study Endpoints

### 4.2.1 Primary Endpoint

Primary Effectiveness Endpoint: improvement in the appearance of any one or more measurement of photoaging damage (fine wrinkles, skin texture, dyschromia/pigment, skin radiance, pore size and overall appearance) by the investigator using the quartile improvement score comparing standard 2D baseline

photograph and the 3 months post final treatment photograph. Reported percent change in improvement.

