#### 7.2 Investigator Evaluations Quartile Improvement Score

Treating Investigators will compare:

- 1. Baseline photographs to one-month post treatment.
- 2. Baseline photographs to three-months post treatment.

A Quartile Improvement Scale will be used to individually score each category: (a) fine wrinkles, (b) skin texture, (c) dyschromia/pigment, (d) skin radiance, (e) pore size and (f) overall appearance.

Investigator Quartile Improvement Score				
Rating	Percentage (%)	Score		
No Improvement	0%	0		
Minor/Mild Improvement	1%-25%	1		
Moderate Improvement	26%-50%	2		
Marked Improvement	51%-75%	3		
Very Significant Improvement	76%-100%	4		

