#### 10. STATISTICS

### 10.1 Statistical Analysis Populations and Demographics

The intent-to-treat (ITT) population will be the primary population for all statistical analyses. The ITT population will include all subjects who received treatment, participated in at least 1 post-baseline evaluation, and were not otherwise disqualified.

Subjects may be removed from the analysis in the case of an AE, SAE, noncompliance, or Investigator decision. The reason for any subject(s) excluded from an analysis population will be documented in a note to file and included in the study report.

Demographic data and baseline characteristics, including age, gender, ethnicity, Fitzpatrick skin type, Glogau rating, and Fitzpatrick wrinkle & elastosis scale rating, will be summarized according to the analysis population for all subjects. For continuous variables, descriptive statistics including number of subjects (N), mean, median, standard deviation (SD), minimum (MIN) and maximum (MAX) values will be presented. For categorical variables, the count and percentage of each category will be provided. The denominator for all percentages will be the number of subjects with non-missing data at the given visit for each respective study treatment, unless otherwise indicated.

The sample size determination of this study is based on the Sponsor's recommendations to quantify the effectiveness and safety of the CLEAR + BRILLIANT TOUCH® diode laser 1440-nm and 1927-nm Laser in the context of this study. Power calculations were performed based on estimates for expected mean change and variance in overall appearance at 3 months as rated by the Investigator using the Quartile Improvement Scale from study 12-133-CBP-F ('Evaluation of the skin after treatment with the Clear + Brilliant 1927-nm wavelength laser by means of the VISIA-CA Imaging System'). The power calculations demonstrated a sample size of 25 has greater than 95% power to reject the null hypothesis (change from baseline=0) for the primary efficacy endpoint. Thus, up to 30 subjects will be enrolled to account for potential drop-out.

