#### 10.2.2 Additional Analysis

Additional analysis will be provided as following:

For IQIS (0-4), the mean score will be compared to a constant value of 0 to test the null hypothesis that there is no improvement after the product use, using the method described in the SAP table.

For GAIS and subject satisfaction data, a binomial (sign) test will be performed to test if the proportion of the combined designated favorable responses (Very Much Improved, Much Improved, and Improved for GAIS; Very Satisfied and Satisfied for subject satisfaction) is equal to the combined designated unfavorable responses.

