#### **Statistical Analysis Plan Table**

Evaluation	Change from baseline	Notes/Interpretation
Investigator	The mean score (0-4) will	Significantly greater than 0
Quartile	be compared to the	indicates improvement.
Improvement	constant 0, using Wilcoxon	
Score	signed rank test	
SAEs	NA	Zero or low number of SAEs is
		favorable
Tolerability	NA	Lower score indicates better
parameters		tolerability
VAS	NA	Lower score indicates better
		tolerability
Biopsy parameters	NA	Descriptive statistics only
Individual	NA	A binomial test (sign test) P value
response data		will be provided. A higher
(GAIS and		percentage of combined favorable
satisfaction)		responses with a significant P
		value indicates positive subject
		perceptions of the test material.
Blinded	The mean score (0-4) will	Significantly greater than 0 indicates
Investigators	be compared to the	improvement.
	constant 0, using Wilcoxson	
	signed rank test	

All statistical tests will be 2-sided at significance level alpha=0.05 unless specified otherwise. *P* values will be reported to 3 decimal places (0.000).

No multiple testing corrections will be considered in the study. Statistical analyses are performed using SAS software version 9.4 (SAS Statistical Institute). The statistical results will be sent to the Sponsor along with raw data in a Microsoft Excel document at completion of the study.

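### The primary endpoint can be met on any one of six scored categories; no deciding variable is named, multiplicity correction is ruled out, and the trial was sized on overall appearance alone

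*Combined protocol and SAP*

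**What the plan says.** Section 4.2.1 sets the primary endpoint as "improvement in the appearance of any one or more measurement of photoaging damage", judged from baseline and 3-month photographs. The synopsis says "improvement in the appearance of at least one measurement of photoaging damage". The six items are fine wrinkles, texture, pigment, radiance, pore size and overall appearance. Section 7.2 states: "A Quartile Improvement Scale will be used to individually score each category". Scores run from 0 (no improvement) to 4, with no score for worsening.

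For the analysis, Section 10.2.2 says that "the mean score will be compared to a constant value of 0 to test the null hypothesis that there is no improvement", and the SAP table assigns the Wilcoxon signed rank test. Neither place names a category, an average over categories, a per-subject responder variable or a decision rule. The notes under the SAP table add: "All statistical tests will be 2-sided at significance level alpha=0.05 unless specified otherwise", and "No multiple testing corrections will be considered in the study".

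Section 10.1 bases the power calculation on "estimates for expected mean change and variance in overall appearance at 3 months as rated by the Investigator". It then reports that 25 subjects give "greater than 95% power to reject the null hypothesis (change from baseline=0) for the primary efficacy endpoint".

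**The concern.** The endpoint definition, the test and the sample-size basis describe three different things. Two readings of the endpoint are open.

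1. **Group level.** Each category is tested at 0.05 and a significant result on any of the six is enough. False primary success is then more likely than with one test, and correction is expressly excluded.
2. **Per subject.** A subject counts as improved if at least one of six scores is non-zero. This is one variable, so there is no multiplicity across categories. But Section 10.2 plans no analysis of that proportion and gives no reference value for it, and Section 10.1 did not power it.

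Under the first reading, success could rest on pore size alone with no significant result on overall appearance. Under either reading, the analysis that decides the trial could be settled after the data are seen. The scores come from unblinded treating investigators in a study without a control group, so fixing the deciding variable in advance is one of the few safeguards available.

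**Working it through.** **Plan's own figure.** Section 10.1 gives n=25, power above 95% and up to 30 enrolled, but not the expected mean or SD. The power cannot be reproduced, only back-solved. For exactly 95% at two-sided 0.05, d = (1.960 + 1.645)/√25 = 0.721 by the normal approximation, or 0.752 by the noncentral t. The claim therefore implies a standardised effect of at least about 0.72 to 0.75 on overall appearance. Since overall appearance is one of the six categories, the figure is a lower bound on power for an uncorrected any-of-six rule. It is not the power of the endpoint as defined.

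**Symmetric benchmark.** Inputs: six tests (Section 7.2), two-sided 0.05, no correction (SAP table). Counting only false improvement, one test errs in 2.5% of trials.

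- Independent: 1 − 0.975^6 = 14.1%.
- Equicorrelated normal statistics, simulated: 10.4% at correlation 0.5 and 5.4% at 0.9.

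The correlations are assumptions; the documents give none.

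**On the 0-4 scale.** No score is negative, so k non-zero scores give an exact two-sided signed rank p of 2/2^k, whatever their size. k=5 gives 0.0625 and k=6 gives 2/64 = 0.031. A category is significant once six subjects score above 0.

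Let p be the chance of a non-zero score in a category when there is no true effect (the stray rate, an assumption). Then:

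- one category = P(Bin(n, p) ≥ 6);
- any of six, independent = 1 − (1 − one category)^6;
- any of six at correlation 0.9 = simulation with latent normal scores, 60,000 trials.

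| n | Stray rate | One category | Any of six, correlation 0.9 | Any of six, independent |
|---|---|---|---|---|
| 25 | 5% | 0.1% | 0.5% | 0.7% |
| 25 | 10% | 3.3% | 10.5% | 18.4% |
| 25 | 20% | 38.3% | 66.5% | 94.5% |
| 30 | 5% | 0.3% | 1.4% | 2.0% |
| 30 | 10% | 7.3% | 20.3% | 36.6% |
| 30 | 20% | 57.3% | 83.3% | 99.4% |

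The any-of-six rule multiplies the single-category rate about 3 to 6 times at stray rates of 5% to 10%, and about 1.5 to 2.5 times at 20%.

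**Per-subject reading.** With no true effect, the share of subjects labelled improved is 1 − (1 − p)^6 if categories are independent: 26.5%, 46.9% and 73.8% at stray rates of 5%, 10% and 20%. At correlation 0.9 it is 10.0%, 18.2% and 32.5%.

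**The case against.** - **No success threshold is stated.** The endpoint text says what is assessed, and the any-of-six decision rule is inferred. This stands in part: the error inflation is conditional on the group-level reading. The per-subject reading escapes it but has no planned analysis, so the primary variable is undefined either way.
- **Section 10.2.1 commits to descriptive summaries of the scores.** A lone positive category would probably be visible beside a null result for overall appearance. That helps a reader of the report, but it does not fix which result is primary.
- **Most of the size on the 0-4 scale comes from testing a scale with no negative score against 0.** This is correct. At a 20% stray rate a single category already rejects in 38.3% of trials at n=25. At 5%, even any-of-six stays below the nominal 2.5%. The across-category increase is a further layer on that separate fault.
- **The practical effect may be small.** One investigator rates all six items from the same photographs, so correlation is probably high. If 40% of subjects scored above 0 in a category (an assumption), that category would be significant in 97% of trials at n=25. The case of one category significant and overall appearance not is possible, but not shown to be likely.
- **The sample size is not shown to be too small.** This stands. The point on power is that it is attributed to a different endpoint.

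**Conclusion.** The concern holds. The plan's wording allows a primary claim on one category without the measure the trial was sized on. It names no deciding variable and excludes correction. Under the group-level reading, false improvement rises from 2.5% to between 5.4% and 14.1% on the symmetric benchmark. On the actual scale, at n=25 and a 10% stray rate, it rises from 3.3% to between 10.5% and 18.4%. These figures rest on assumed correlations from 0.9 down to 0 and, on the 0-4 scale, on an assumed stray rate; the size varies strongly with that rate. That the variable is undefined depends on no assumption. The wording should be changed before the data are seen.

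**What to change.** In the synopsis, Section 4.2.1 and the SAP table, name the investigator's overall-appearance score at 3 months as the single primary variable, and remove the wording that lets any one category suffice. This matches the basis of the power calculation in Section 10.1, so the stated power would then refer to the stated endpoint. Make the other five categories secondary: either with Holm adjustment, starting at 0.05/5 = 0.01 and amending the sentence that excludes multiplicity correction, or reported descriptively. Treat the 1-month endpoint in Section 4.2.2 the same way.

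The cost is wording only; every score is already collected. The downside for the sponsor is that improvement in one other category no longer counts as primary success.

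If an any-of-six rule is preferred, it needs adjusted tests and its own power statement. With Bonferroni at 0.05/6 = 0.0083, and if the planned power was exactly 95%, per-category power at n=25 falls to 83% (normal approximation) or 80% (noncentral t), and 36 to 37 evaluable subjects are needed to restore 95%. A larger true effect would shrink that loss: if the planned power was 99%, it falls to 95%. A per-subject responder endpoint would need a definition, a reference proportion, a test and its own power calculation.

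None of these changes cures the separate problem of testing a scale with no negative score against 0.
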